6.1.2 Secondary Endpoints

The secondary efficacy endpoints of this study are as follows:

- 1) Percentage of subjects forming gallstones within 3, 6, 9, and 12 months from gastrectomy
- ➤ Percentage of subjects with gallstones formation (%) = (The subjects who were identified as having gallstone formation in at least one of the following sites, gallbladder, bile duct, and intrahepatic bile duct, within 3, 6, 9, and 12 months after gastrectomy/Number of subjects analyzed)*100
- 2) Percentage of subjects forming gallstone within 3, 6, and 9 months from gastrectomy as assessed by the external investigator
- Percentage of subjects with gallstone formation (%) = (Based on external investigator's assessment, the subjects who were identified as having gallstone formation in at least one of the following sites, gallbladder, bile duct, and intrahepatic bile duct, within 3, 6, and 9 months after gastrectomy/Number of subjects analyzed)*100
- 3) Percentage of subjects forming biliary sludge within 3, 6, 9, and 12 months from gastrectomy
- ➤ Percentage of subjects with biliary sludge formation (%) = (The subjects who were identified as having biliary sludge formation at least once within 3, 6, 9, and 12 months after gastrectomy/Number of subjects analyzed)*100
- 4) Time to gallstone formation
- The time to gallstone formation is calculated as the time until the early termination or completion after a gastrectomy, if the gallstone has been formed within 12 months resulting in early termination, or at 12 months resulting in completion. Subjects who do not form gallstones until the completion of the clinical study are treated as censoring and their time period until completion is calculated. If subjects are withdrawn within the 12 months after a gastrectomy, they are treated as censoring data and their time period until the withdrawal is calculated.

^{*} In the case of the subjects who are confirmed to have gallstones by the institutional

Form DA-05-03.03 Statistical Analysis Plan

Sponsor: Daewoong Pharmaceutical Co., Ltd.

Protocol No.: DW_UDCA005 English Translation Version

reviewer and are terminated early from the clinical study, to be conservative, they are defined as subjects with gallstone formation regardless of the external investigator's assessment.

- Time to Gallstone Formation
 - Status = 1, if gallstones were formed
 - = 0 (censoring), if gallstones were not formed until last f/u
 - Duration (day) = [Study Completion/Early Termination or Study Completion/ Dropout date (censored), whichever occurs first date of gastrectomy +1]

6.1.3 Exploratory Endpoints

The exploratory efficacy endpoints of this study are as follows:

- 1) Change in the biliary reflux symptoms from baseline at 3, 6, 9, and 12 months
- ➤ Change from baseline at n month = value at n month baseline, n=3,6,9,12
- 2) Percentage of subjects who experienced biliary reflux according to the upper gastrointestinal endoscopy at 3 and 12 months
- ➤ Percentage of subjects with biliary reflux occurrence (%) = (The subjects who experienced biliary reflux at Months 3 and 12 after gastrectomy/Number of subjects analyzed)*100
- 3) Percentage of subjects who showed significantly abnormal AST and ALT values at 6 and 12 months
- Percentage of subjects who were CS for result of AST/ALT (%) = (The subjects who showed significantly abnormal AST and ALT values at 6 and 12 months after gastrectomy/Number of subjects analyzed)*100

6.2 Medical History and Concurrent Disease

6.2.1 Medical History

Medical history is defined as a medical condition currently not persisting out of all collected historical medical conditions including allergies.

6.2.2 Concurrent Disease

Concurrent disease is defined as a medical condition currently persisting out of all collected historical medical conditions including allergies.

6.2.3 Prior Surgery

Prior surgery is defined as all collected surgical operations except gastric cancer surgery.

Protocol No.: DW_UDCA005 English Translation Version

6.3 Prior and Concomitant Medication

6.3.1 Prior Medication

Prior medication is defined as medication whose onset of administration is before taking the first dose of the investigational product.

6.3.2 Concomitant Medication

Concomitant medication is defined as a drug whose onset of administration is after taking the first dose of the investigational product. If the starting or ending date of the administration is incomplete and it is difficult to distinguish the prior/concomitant medication, it is regarded as concomitant medication. If the start date of the administration is after the end of the clinical study, then it is excluded from the concomitant medication.

6.4 Treatment Compliance

Treatment compliance of the investigational product provided to the subject is collected at 3, 6, 9, and 12 months.

Treatment compliance by visit and overall treatment compliance for the investigational product provided to the subject are as follows and are rounded to the nearest two decimal places. Treatment compliance by visit is presented only for the regular visits, and overall treatment compliance is based on all information including withdrawal visits before the end of the study. However, it does not include unscheduled visits after a withdrawal visit.

Treatment compliance is calculated using the following formula:

		Quantity (cap) of the investigational product	
Treatment	compliance	actually taken	× 100
(%) =	_	Quantity (cap) of investigational product to be taken ¹⁾	_

[Treatment compliance by visit] Quantity (cap) of investigational product to be taken = (Prescription date of the investigational product for the visit / If last visit, last visit date** – Prior prescription date of the investigational product) * 2

[Overall treatment compliance] Quantity (cap) of investigational product to be taken = (Last visit** - First prescription date of the investigational product) * 2

¹⁾ Number of investigational product to be taken

^{**} For withdrawn subjects, if only the investigational product is returned without withdrawal visit, apply the clinical study ending date/withdrawal date

Protocol No.: DW_UDCA005 English Translation Version

6.5 SAFETY VARIABLES

6.5.1 Extent of Exposure

In terms of extent of exposure to the investigational product, the total dose (mg), exposure period (days) and average daily dose (mg/day) are calculated as follows:

- ➤ Total dose (mg) = Quantity (cap) of the investigational product actually taken x 300 mg
- > Exposure period (day) = Last visit** First prescription day of the investigational product
 - ** For withdrawn subjects, if only the investigational product is returned without withdrawal visit, apply the clinical study ending date/withdrawal date
- Average daily dose (mg/day) = total dose (mg) / exposure period (day)

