10.2. Dosage and Administration, Method and Period of Administration

All randomly assigned subjects are orally administered with the investigational product twice a day, one capsule at a time, for a total of 52 weeks. The subjects take the investigational product in the morning and evening according to the investigator's instructions and if possible, take it at the same time each day.

[Method of administration by treatment group]

Treatment group**	atment group** Method of administration	
Placebo	One capsule each of placebo for DWJ1319 in the morning	Morning: ○,
Flacebo	and evening	Evening: ○
DWJ1319 300 mg	One capsule each of placebo for DWJ1319 in the morning	Morning: ○,
	and DWJ1319 in the evening	Evening: •
DWJ1319 600 mg	One capsule each of DWJ1319 in the morning and	Morning: ●,
DW31319 000 Hig	evening	Evening: ●

Confidential Page 20 of 51

o: Placebo of DWJ1319, ●: DWJ1319

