4. INVESTIGATIONAL PLAN

4.1 Overall Study Design and Plan

A multi-centered, randomized, double-blind, placebo-controlled, phase 3 clinical study. The subjects are patients who have been diagnosed with gastric cancer and underwent gastrectomy for treatment. Screening will be conducted on subjects who gave an informed consent to participate in the clinical study. Subjects who meet the inclusion criteria and do not meet exclusion criteria will be randomly assigned to DWJ1319 300 mg (DWJ1319 300 mg, once a day), DWJ1319 600 mg (DWJ1319 300 mg, twice a day), or placebo (1: 1: 1). For randomization, stratified randomization using the study site, the lymph node resection range (D1+, D2), and the type of gastrectomy as the stratification factors will be performed and randomization will be performed within 2 weeks from gastrectomy. During the study period, the subjects will visit the study site at screening, randomization (Day 1) and at 3-month intervals after the administration of investigational product (at 3, 6, 9, and 12 months) to undergo protocol-specified tests and procedures at each visit. However, any subject with formation of gallstone confirmed during the treatment period will terminate the study at the time of confirmation.

Visit 1	Visit 2	Visit 3	Visit 4	Visit 5	Visit 6		
Until week -2	Day 1	3 months±1 week	6 months±1 week	9 months±1 week	12 months±1 week		
Screening	Randomizatio n	Treatment period					

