4.3 Dosage, Administration and Schedule

All randomly assigned subjects are orally administered with the investigational product twice a day, one capsule at a time, for a total of 52 weeks. The subjects take the investigational product in the morning and evening according to the investigator's instructions and if possible, take it at the same time each day.

Protocol No.: DW_UDCA005 English Translation Version

[Method of administration by treatment group]

Treatment group	Method of administration	Study drug
Placebo	One capsule each of placebo for DWJ1319 in the morning	Morning: ○,
1 lacebo	and evening	Evening: ○
DWJ1319 300 mg	One capsule each of placebo for DWJ1319 in the morning	Morning: ○,
DW31319 300 Hig	and DWJ1319 in the evening	Evening: ●
DWJ1319 600 mg	One capsule each of DWJ1319 in the morning and	Morning: ●,
DVV31319 000 111g	evening	Evening: ●

o: Placebo for DWJ1319, ●: DWJ1319

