9.1 Extent of Exposure

In terms of extent of exposure to the investigational product, for the Safety Set, the total dose (mg), exposure period (days) and average daily dose (mg/day) are presented with descriptive statistics (number of subjects, mean, standard deviation, median, minimum, and maximum values) for each treatment group.

A summary of the data is presented in the following tables.

- T. Extent to Exposure (Safety Set)

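### The SAP exposure formula gives every capsule 300 mg, placebo included, so total dose and average daily dose are wrong for the placebo and 300 mg arms in one descriptive table

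*Protocol*

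**What the plan says.** SAP section 6.5.1 (Extent of Exposure) sets total dose in mg equal to "Quantity (cap) of the investigational product actually taken x 300 mg". It then sets "Average daily dose (mg/day) = total dose (mg) / exposure period (day"), where the exposure period runs from the first prescription day to the last visit. Neither line depends on treatment arm or capsule type.

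SAP section 9.1 reports the results for the Safety Set by treatment group: "the total dose (mg), exposure period (days) and average daily dose (mg/day) are presented" with descriptive statistics.

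On dosing, SAP section 4.3 states that "All randomly assigned subjects are orally administered with the investigational product twice a day, one capsule at a time". Protocol section 10.2 says the same and has the same regimen table:

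- Placebo arm: placebo morning and evening.
- 300 mg arm: the row begins "One capsule each of placebo for DWJ1319 in the morning", with DWJ1319 in the evening.
- 600 mg arm: DWJ1319 morning and evening.

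SAP section 4.1 describes the active arms as "DWJ1319 300 mg (DWJ1319 300 mg, once a day") and "DWJ1319 600 mg (DWJ1319 300 mg, twice a day"). Protocol sections 6.1 and 6.2 put 300 mg of ursodeoxycholic acid in the DWJ1319 capsule and only matching placebo in the comparator capsule.

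**The concern.** The mg factor belongs to the active capsule, but the formula applies it to every capsule. Two of the three arms take placebo capsules daily, so their dose in mg is overstated. The exposure table is where a reader sees how much drug each arm received. In a trial with two active doses and placebo, it should show three separated levels. As defined, it shows one common level, and it shows placebo subjects receiving active drug.

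**Working it through.** **Does the term include placebo capsules?** The formula would be harmless if investigational product meant active capsules only. The documents rule that out in three places.

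1. The protocol synopsis lists the placebo comparator under its investigational product entry, and SAP section 4.3 has all randomised subjects taking the investigational product.
2. SAP section 6.4 uses the same capsule quantity as the numerator of compliance, over days × 2 in every arm. If it counted active capsules only, a fully compliant subject would score 0/2 = 0% in the placebo arm and 1/2 = 50% in the 300 mg arm. Both fall below the 80% limit in protocol section 13.4, which would remove both arms from the per-protocol set.
3. The Full Analysis Set and Safety Set (SAP sections 5.3 and 5.5) require at least one administration of investigational product. An active-only meaning would exclude every placebo subject.

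So the capsule count in section 6.5.1 includes placebo capsules.

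**Inputs.** Two capsules a day in every arm (SAP 4.3). Active capsules per day: 0, 1 and 2 (same table). 300 mg per active capsule (protocol 6.1). Treatment period of 52 weeks = 364 days (SAP 4.2).

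**The plan's own target.** Active capsules per day × 300 mg gives 0, 300 and 600 mg/day, which matches the assigned doses in SAP section 4.1.

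**The formula as written, full compliance.** 364 × 2 = 728 capsules. 728 × 300 = 218,400 mg. 218,400 / 364 = 600 mg/day, in each arm.

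| Arm | Formula, total mg | Formula, mg/day | Active drug, total mg | Active drug, mg/day |
|---|---|---|---|---|
| Placebo | 218,400 | 600 | 0 | 0 |
| 300 mg | 218,400 | 600 | 364 × 1 × 300 = 109,200 | 300 |
| 600 mg | 218,400 | 600 | 364 × 2 × 300 = 218,400 | 600 |

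**Lower compliance.** Let c be overall compliance as a fraction. The compliance denominator and the exposure period use the same dates, so average daily dose as defined is 2 × c × 300 = 600c mg/day in every arm. At an assumed c = 0.9 it is 540 mg/day, and at c = 0.8 it is 480 mg/day. With misses spread evenly over morning and evening, the active dose at c = 0.8 is 0, 240 and 480 mg/day. As written, then, the average daily dose is compliance rescaled and carries no information on assigned dose.

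**How well a pooled count can recover the active dose in the 300 mg arm.** At c = 0.8, missed capsules are 0.2 × 728 = 145.6. If all of them were evening (active) capsules, the active dose is 300 × (364 − 145.6) / 364 = 180 mg/day. If all were morning (placebo) capsules, it is 300 mg/day. The even-split value is 240 mg/day, so the approximation is off by at most 60 mg/day for that subject. At c = 0.9 the range is 240 to 300 mg/day.

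**The case against.** The best case on the other side accepts the arithmetic and disputes its reach. Four parts of it deserve an answer.

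- **Reach.** The formula feeds one descriptive table with no test attached. A reader might infer that any dose-related or exposure-adjusted reading of safety becomes invalid. The documents do not support that. SAP sections 9.2.1 to 9.3.1 summarise adverse events, laboratory values and vital signs by treatment group, and none of these divides by mg or uses mg as a covariate. Comparisons by assigned arm do not pass through this formula. This part stands.
- **Certainty.** It is also tempting to say that the wrong figures will be published. That assumes the formula is programmed literally. An average near 600 mg/day in a column headed placebo would be conspicuous once the code is released, and a programmer may correct it. This stands as to likelihood. It does not rescue the text, because the SAP gives the programmer no rule to apply instead.
- **Size.** The 600 mg/day figure is the full-compliance case and falls in proportion to compliance. Total dose is equal across arms only when compliance and time on treatment are equal. Subjects with a confirmed gallstone leave early, so group means of total dose could differ for that reason alone, but such a difference would not reflect assigned dose.
- **Remedy.** Counting morning and evening returns in the 300 mg arm alone is not workable, because sites are blinded (protocol 10.5.2, SAP 4.4.2) and cannot know who is in that arm. This stands and shapes the fix.

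**Conclusion.** The concern holds within narrow limits. SAP section 6.5.1, followed as written, gives a wrong total dose and a wrong average daily dose for two of the three arms. At full compliance the 300 mg arm is shown at 600 instead of 300 mg/day, the placebo arm at 600 instead of 0 mg/day, and the 600 mg arm correctly. The 2-fold overstatement in the 300 mg arm persists at lower compliance if misses split evenly between morning and evening. No other section of the protocol or SAP corrects this.

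The damage is limited to those two descriptive rows of the Safety Set exposure table. Exposure days do not use the 300 mg factor, and the compliance formula rightly counts all capsules. The efficacy analyses, the sample size and the by-arm safety comparisons do not use the quantity at all. The conclusion assumes literal programming, two capsules dispensed per day in every arm, and 364 days for the worked totals. The daily figures do not depend on the 364.

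**What to change.** Replace the total dose line in SAP section 6.5.1 with a total active dose defined by arm: pooled capsules taken × 0 mg in the placebo arm, × 150 mg in the 300 mg arm and × 300 mg in the 600 mg arm. Apply it after unblinding, and leave the average daily dose formula as it is. Add capsules taken as a separate row of the exposure table, so that treatment exposure stays visible in all arms.

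The cost is one formula and one table row, with nothing changed for sites or subjects. The downside is that 150 mg per pooled capsule is an approximation: it assumes missed capsules split evenly between morning and evening, and the SAP should state this. Evening capsules can be counted directly only if morning and evening returns were recorded separately for all subjects. The documents describe collecting unused product and computing compliance from a pooled count, and do not mention separate counts, so the by-arm factor should be the default.

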6.5.2 Treatment-Emergent Adverse Events (TEAEs)

The treatment-emergent adverse events (TEAEs) of the adverse events collected during the clinical study are evaluated, and the TEAEs are as follows:

- Adverse events that occurred after the "first dose of the investigational product after randomization"
- Among the symptoms that preceded the "first dose of the investigational product after randomization", adverse events with worsened severity following the "first dose of the investigational product after randomization"

However, if the occurrence date of the adverse event is missing or incomplete and, it is unclear if it had occurred pre or post "dose of the investigational product after randomization", then the event is considered as a TEAE.

[Severity of Adverse Events]

- 1) Mild: Showing symptoms or signs but without hindrance to daily life
- 2) Moderate: The degree to which routine activities are restricted and sufficiently inconvenienced
- 3) Severe: To the extent that daily activities cannot be carried out

[Relevance to Investigational Product]

- 1) Definitely related
- 2) Probably related
- 3) Possibly related
- 4) Probably not related, Unlikely
- 5) Definitely not related, None
- 6) Unknown, Unassessable

Protocol No.: DW_UDCA005 English Translation Version

6.5.3 Adverse Drug Reaction

TEAEs' causal relationship to the investigational product is defined in the following Adverse Drug Reactions (ADRs) categories: Definitely related, Probably related, Possibly related, and Unknown or Unassessable.

6.5.4 Serious Adverse Event

Serious Adverse Event (SAE) means one of the following adverse events or adverse drug reactions that occur at any dose of an investigational product.

- In case of death or life-threatening
- In case where hospitalization is necessary or hospital stay needs to be extended
- In case of permanent or significant failure or degradation of function
- In case of malformations or abnormalities in the fetus

6.5.5 Vital Signs

Vital signs (blood pressure, pulse) are measured at each visit. Pulse and blood pressure should be measured after the subject has been sitting for 5 minutes, and always on the same arm for evaluation.

6.5.6 Laboratory Data

Laboratory tests are carried out using the Central lab and are performed in a fasted state at Visits 1, 4 and 6 or at the time of early termination/withdrawal. If screening results do not meet the inclusion/exclusion criteria, they may be retested only once. Women of childbearing age are checked for possibility of pregnancy by taking the urine hCG test at Visit 1. In addition, if it is deemed necessary by the investigator's judgment, further testing is possible.

Laboratory test items are as follows.

Hematology	WBC, RBC, Hemoglobin (Hb), Hematocrit (Hct), Platelet count, WBC differential count (Neutrophil, Lymphocyte, Monocyte, Eosinophils, Basophils)
Biochemical test	Glucose, Total protein, Albumin, Total cholesterol, Triglyceride, Total bilirubin, alanine transaminase (ALT), aspartate transaminase (AST), alkaline phosphatase (ALP), blood urea nitrogen (BUN), gamma-glutamyl transferase (γ-GTP), Uric acid, Creatinine, sodium, potassium, chloride, calcium, HbA1c*, eGFR
Urinalysis	Bilirubin, urobilinogen, Blood, Glucose, pH, Protein, Specific Gravity
Pregnancy test**	Urine HCG

Protocol No.: DW_UDCA005 English Translation Version

* HbA1c: It is performed once during the screening and if there is a test result within the last 3 months, it can be replaced for the screening test.

In addition, only the liver function tests (ALT, AST, ALP, γ -GTP and total bilirubin) among the biochemical tests are performed at Visits 3 and 5.

6.5.7 Physical Examination

Physical examination is performed at Visits 1, 4 and 6 or at the time of early termination/withdrawal. The investigator will perform a physical examination on the subject through an interview, examination, palpation, and auscultation and write the results on the case record. Examination categories include general appearance, skin/mucosa, lymphatic system, head/neck, eye/ear/nose/throat, gastrointestinal, cardiovascular, respiratory, neurological and musculoskeletal systems. The symptoms due to the underlying disease (gastric cancer and gastrectomy) of the clinical study are not collected.

^{**}Pregnancy test: It is performed only for women of childbearing age.

Protocol No.: DW_UDCA005 English Translation Version

Page 23 of 37

7. DISPOSITION AND PROTOCOL DEVIATIONS

7.1 Subject Disposition

For the screening set, the frequency of the subjects who participated in the clinical study and the subjects who were randomized are presented. The subjects who were eliminated from the screening and the reason for their elimination are presented with frequency and percentage. For the randomized set, the frequency and percentage of the subjects who were administered the investigational product and the subjects who were terminated early or withdrawn from the clinical study are presented. For the subjects who were withdrawn, the reasons for withdrawal are presented with frequency and percentage. Also, a list of the subjects who have been withdrawn is complied.

A summary of the data is presented in the following table, list, and figure.

- T. Study Disposition (Screened Set)
- T. Subject Disposition by Site (Screened set)
- L. Discontinued Subjects (Randomized Set)

